13.1. Primary efficacy

The primary efficacy endpoint is the change from baseline of the Best Corrected Visual Acuity (BCVA) reported with LogMAR at 1.5 years post-treatment, in second-affected/not-yet-affected eyes of ND4 LHON subjects with vision loss up to one year. The change from baseline (Visit 2) in primary (second-affected/not-yet-affected) eyes receiving GS010 and placebo will be the primary response of interest. LogMAR BCVA will be used to represent BCVA.

The definition of the primary eye (the second/not yet affected eye) is based on the vision loss duration. The second/not yet affected eye is the eye with the smallest vision loss duration or with a vision loss duration equal to 0. For subjects who report simultaneous onset of vision loss in both eyes, the right or left eye will be selected randomly to serve as the second-affected/not-yet-affected eye. If the second affected eye did not receive the correct treatment (as set in the randomization scheme) then the subject will be assigned to the arm corresponding to the randomized treatment.

13.1.1. Primary efficacy variable & derivation

Visual acuity (EDTRS and LogMAR)

ETDRS score is calculated by the examiner and written on the source documents and entered in the eCRF.

One Early-Treatment Diabetic Retinopathy Study (ETDRS) line equates to 0.1 LogMAR, and 1 ETDRS letter equates to 0.02 LogMAR.

On chart and off chart

On-chart subjects are able to read at least three ETDRS letters on a single line of the ETDRS chart at 1 meter distance and will thus have an ETDRS score, Snellen visual acuity, and LogMAR visual acuity based on the letters/lines read on the ETDRS chart at 4- and 1-meter distances.

Off-chart subjects are not able to read at least three ETDRS letters on a single line of the ETDRS chart at 1 meter distance and thus will not have an ETDRS score. Off-chart subjects will be tested for count fingers (CF) or hand motion (HM) visual acuity per the SOP for Ocular and Vision Testing. The LogMAR visual acuity will be assigned to the validated Lange scale LogMAR value for CF and HM (C. Lange et al. Graefes Arch Clin Exp Ophthalmol (2009) 247:137-142):

- +2.0 LogMAR for CF
- +2.3 LogMAR for HM

For light perception (LP) +4.0 LogMAR is assigned

For no light perception (NLP) +4.5 LogMAR is assigned.

13.1.2. Timing of primary analysis

Primary endpoint analysis will be performed as soon as the last subject completes the 1.5-year LogMAR assessment and data are cleaned. All subjects will be recruited and followed for at least 1.5 years except in case of premature withdrawal. The study will be formally unmasked for the efficacy analysis at 1.5 years to allow an early registration, if results meet the expectations. The study will continue to its scheduled end (5 Years).

13.1.3. Handling of missing data

To address the impact of COVID-19 on study integrity, the LogMAR of Patients without assessment in the protocol-defined window of time [518-699 days] will be imputed by a LogMAR defined by clinical decision during the data-review before the database lock. If data remains missing, it will be imputed with Last observation carried forward method (LOCF).

Number of missing data and a listing with imputed values will be provided.

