### 6.2.1 Clinical Development Program for GS010

GS010 is being developed for the treatment of vision loss in LHON due to the G11778A *ND4* mitochondrial mutation. The clinical development of GS010 has included:

- Safety and tolerability study with dose-exploration

GS-LHON-CLIN-01: A Phase I/II, open label, dose-escalation safety and tolerability study. The maximal well-tolerated dose of [REDACTED] [REDACTED] per eye was selected for further study.

- Unilateral administration efficacy study in subjects with vision loss up to six months

GS-LHON-CLIN-03A RESCUE: A Phase III randomized, sham-controlled, GS010 (dose [REDACTED]) administration study in subjects with vision loss for up to six months.

- Unilateral administration efficacy study in subjects with vision loss for more than six months and up to 1 year

GS-LHON-CLIN-03B REVERSE: A Phase III randomized, sham-controlled, GS010 (dose [REDACTED]) administration study in subjects with vision loss for more than six months and up to 1 year.

LHON is a bilateral disease. Often the eyes of a given subject are affected sequentially and potentially the elapsed time between onset of vision loss and treatment administration may impact the presence and magnitude of the treatment effect in a neurodegenerative disease such as LHON. As such, the next step in the clinical development plan for GS010 is to assess the safety and efficacy of bilateral administration of intravitreal GS010 and to determine if a difference exists in the treatment of the first- and second-affected or not-yet-affected eyes.

Recent GS010 study results have shown that the benefit from GS010 is more pronounced after 1-year post injection. Preliminary data from the REVERSE study demonstrated that there is an improvement from baseline in BCVA at Week 72 of +15 ETDRS letters ( $-0.295$  [Standard Error  $\pm 0.063$ ] LogMAR;  $p < 0.0001$ ) and of +12 ETDRS letters ( $-0.246$  [Standard Error  $\pm 0.063$ ] LogMAR;  $p = 0.0003$ ) in GS010 treated eyes and sham treated eyes, respectively (data on file). This improvement in BCVA was less marked at Week 48 with +11 letters and +10 letters in GS010 treated eyes and sham eyes, respectively (data on file). This sustained and increased improvement in BCVA over time supports a read out of the primary endpoint in the REFLECT study at 1.5 year-post treatment.

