#### *16.4.1.14 Handling of Missing Data*

In case of missing data up to and including 1.5 years in the primary (second affected/not yet affected) eye, multiple imputation will be used as the primary method of imputation for the following endpoints: BCVA measured in LogMAR, Pelli-Robson CS, and HVF 30-2.

Multiple imputation using ten imputations of missing endpoint value will be produced using SAS PROC MI followed by PROC MIANALYZE for both missing at random and missing not at random missing data mechanisms. The seed used to begin random number generation will be 20190219. The Markov chain Monte Carlo method will be used to compute 10 full imputation data sets using the following baseline predictor variables: baseline of endpoint being imputed, duration vision loss in eye, age and gender. Baseline LogMAR and baseline contrast sensitivity will be included in all models.

Last observation carried forward method (LOCF) will be used as secondary method of imputing missing data analysis.

In summaries of data by visits for ITT or mITT populations, the average of the multiply imputed values from PROC MI, rounded to the level of the non-missing data, will be used.

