3.4. Changes to analysis from protocol

1. To address the impact of COVID-19 on study integrity, an extension of the protocol-defined window of time for performing the endpoint has been decided during the data-review before the database lock. Data collected before or after 1.5 year was assessed by the data review committee as relevant and representative of the missing 1.5-year data. Time windows are specified in SAP section 5.3.
2. In the protocol (section 16.4.1.14): In case of missing data up to and including 1.5 years in the primary (second affected/not yet affected) eye, multiple imputation will be used as the primary method of imputation for the following endpoints: BCVA measured in LogMAR, Pelli-Robson CS, and HVF 30-2.

Approach defined in protocol section changed to approach in SAP section 13.1.3: Last observation carried forward method (LOCF) will be used of imputing missing data. In this disease, outside of the very initial phase, BCVA worsen slowly over time (natural history of the disease), whereas active treatment improves BCVA over time, LOCF will therefore tend to favor the placebo eye group and disadvantage the treated eye group.

3. In the protocol (section 16.4.1.12): Sensitivity Analysis: For ITT and mITT analyses, missing data will be imputed using multiple imputations.

Modify by (section 6.4.1.14): Sensitivity analyses of the primary endpoint will be conducted only on observed data (data without imputed values) up to 1.5 years using a MMRM model.

4. Removal of the exploratory analysis coverage (section 16.4.2.4.3) because this analysis is similar to the MMRM model analysis.
5. Removal intra-subject analyses of difference at 1.5, 2, 3, 4 and 5 years post-treatment, between first affected eyes and second-affected/not-yet-affected eyes treated with GS010 (part of objective 5), based on FDA recommendation: "Although use of the contralateral eye to which the GT product is not administered as a control may potentially be considered, it is generally not recommended" Protocol section and analyses described that are not done in SAP:

13.1.6 – Duration of disease is no longer used

13.1.5 – Change of supportive analyses

13.2.3– No more time to event analyses

13.2.3– AUC is no longer done

6. Planned analyses

The following analyses will be performed for this study:

- Analyses for Data Safety Monitoring Board (DSMB) meetings
- Primary efficacy analysis at 1.5 years
- Post-Treatment Follow-Up Period 2 Analyses at 3 and 4 years

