13.2.1. Secondary efficacy variables & derivations

Change in LogMAR BCVA

The first secondary efficacy endpoint is the change from baseline in LogMAR BCVA to each follow-up visit (after 1.5 years) (see section 13.1.4) with the same missing data imputation strategy.

For 5-year analysis, additional supportive analyses will be done:

- Using last available LogMAR value
- Same analysis on PP5Y population.

Response status

The second secondary efficacy endpoint is the responder rate.

For subjects discontinued prior to the time of analysis or with missing data, LOCF imputed data will be used.

Three definitions of responders are given below:

Definition 1 – Gainer eyes:

Eyes whose LogMAR BCVA improves (i.e. decrease) by ≥ 0.3 LogMAR (equivalent to a gain of ≥ 15 ETDRS letters) compared to baseline, i.e. an eye is a responder if: $\text{LogMAR at interest timepoint} - \text{LogMAR at Baseline} \leq -0.30$.

Definition 2 – Stabilized eyes:

Eyes whose LogMAR BCVA does not worsen (i.e. does not increase) by ≥ 0.3 LogMAR (equivalent to an eye that loses ≤ 15 ETDRS letters) compared to baseline, i.e. an eye is a responder if: $\text{LogMAR at interest timepoint} - \text{LogMAR at Baseline} \leq 0.30$.

Definition 3 - Not legally blind:

Eyes whose LogMAR visual acuity is < 1.0 at interest timepoint (i.e. better than LogMAR 1.0, equivalent to better than Snellen acuity of 20/200).

This third definition of interest is exploratory given the precipitous vision loss experienced by the majority of ND4 LHON subjects. Any significant difference in the percentage of second-affected/not-yet-affected responder eyes, receiving GS010 compared to placebo, is pertinent considering the seriousness of the visual impairment.

The response status will be assessed at eye and subject level.

For subject response, the best response observed in either eye will be considered (LogMAR measured on both eyes will not be considered).

Parameters measured with SD-OCT

The changes from baseline at each time point in the following parameters as measured by the SD-OCT:

- Total and Temporal Quadrant Retinal Nerve Fiber Layer (RNFL) thickness;
- Papillo Macular Bundle (PMB) RNFL thickness
- Ganglion Cell Layer macular volume
- ETDRS macular volume

HVF 30-2

The changes from baseline at each time point the following parameters of standardized, automated visual fields obtained with the HVF Analyzer II (HVF 30-2):

- Mean deviation
- Foveal threshold sensitivity
- Pattern standard deviation

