13.2.2. Missing Data Methods for Secondary Efficacy Variable(s)

Missing data will be imputed using the control-based imputation described in section 13.1.3 for BCVA measured in LogMAR,

Total score and individual subscale scores form the VFQ-25, composite score and individual domain score as well as categorical secondary efficacy endpoints will not be imputed.

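### Missing 1.5-year LogMAR values are filled by a clinical decision with no stated rule and then by LOCF, in place of the protocol's multiple imputation; the claim that this works against GS010 is not guaranteed, and no MNAR analysis remains

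*SAP*

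**What the plan says.** Protocol 16.4.1.14 states that for missing data up to 1.5 years in the primary eye "multiple imputation will be used as the primary method of imputation for the following endpoints", LogMAR BCVA among them. It specifies ten imputations under both MAR and MNAR, from baseline predictors, and gives LOCF a secondary role.

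SAP 13.1.3 replaces this with two steps. If there is no assessment in days 518 to 699, the LogMAR "will be imputed by a LogMAR defined by clinical decision during the data-review before the database lock". If the value is still missing, LOCF applies. Imputed values are to be counted and listed.

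SAP 3.4, item 2, declares the change. Its reason is that untreated acuity declines slowly after the very initial phase while treated eyes improve, so "LOCF will therefore tend to favor the placebo eye group and disadvantage the treated eye group". Item 3 replaces the multiple-imputation sensitivity analysis with an MMRM on observed data only (SAP 13.1.6).

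For secondary endpoints, SAP 13.2.1 applies the same strategy to LogMAR change after 1.5 years. For responder status it says: "For subjects discontinued prior to the time of analysis or with missing data, LOCF imputed data will be used". SAP 13.2.2 says: "Missing data will be imputed using the control-based imputation described in section 13.1.3", and then that categorical secondary endpoints are not imputed.

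**The concern.** The primary contrast can depend on values for which the plan states no selection rule. SAP 13.1.3 does not say which visits qualify, who decides, or that they are masked to arm. What is left is filled by a single carried-forward value, which the ANCOVA treats as observed.

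The SAP relies on LOCF being conservative. That rests on control eyes worsening, and the protocol's own data do not show this. Protocol 6.2.1 reports Week 72 gains in REVERSE of 15 letters (-0.295 LogMAR) with GS010 and 12 letters (-0.246) with sham, and adds: "This improvement in BCVA was less marked at Week 48 with +11 letters and +10 letters in GS010 treated eyes and sham eyes, respectively". If control eyes also improve, LOCF takes improvement away from both arms, and the sign of the bias depends on which arm has more missing data.

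The SAP's reasoning also excepts the very initial phase. Eligible primary eyes have 0 to 365 days of vision loss and include eyes not yet affected, so some may fall within that exception.

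**Working it through.** **The plan's own figure.** Inputs from Protocol 16.2 and SAP 3.2: difference 0.3, SD 0.50, two-sided alpha 0.05, power 80%. The normal approximation gives 2 × (0.50 × (1.960 + 0.842) / 0.3)² = 43.6, so 44 per arm. The noncentral t gives 79.5% power at 44 and 80.4% at 45. The stated 45 per arm is reproduced. The standard error of the contrast is 0.50 × √(2/45) = 0.105.

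**LOCF bias.** Let mG and mP be the fractions imputed in the GS010 and placebo arms, and dG and dP the mean LogMAR change after the last observation (negative is improvement). LOCF omits that later change, so the bias in GS010 minus placebo is mP × dP − mG × dG. A positive value is against GS010.

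The inputs are REVERSE means from Protocol 6.2.1, at 0.02 LogMAR per letter:
- Last value near Week 48: dG = −(15 − 11) × 0.02 = −0.08; dP = −(12 − 10) × 0.02 = −0.04.
- Last value near baseline: dG = −0.295; dP = −0.246.

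| Missing | Last value near Week 48 | Last value near baseline |
|---|---|---|
| 5% in both arms | +0.002 | +0.002 |
| 5% in GS010 only | +0.004 | +0.015 |
| 5% in placebo only | −0.002 | −0.012 |

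The sign turns in favour of GS010 when mP/mG exceeds dG/dP: 0.08/0.04 = 2.0 near Week 48, and 0.295/0.246 = 1.2 near baseline.

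The largest value, 0.015, is 5% of the 0.30 target and 0.14 standard errors. With 20% missing in one arm only (an assumption), the near-baseline figures become 0.20 × 0.295 = 0.059 against GS010 or 0.20 × 0.246 = 0.049 in its favour.

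If placebo eyes did worsen, say by +0.05 (an assumption), every missingness pattern tested ran against GS010. The SAP's conclusion therefore holds under its premise; it is the premise that conflicts with REVERSE.

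**Precision.** If filled values carry no information beyond the completers, the standard error is understated by the factor √(1 − m). At 5% missing this is 0.975, or about 2.5%; at an assumed 20% it is 0.894, or about 11%.

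**Near-normal eyes.** Protocol 6.1 cites a series in which 98% of eyes ended at 20/200 or worse, that is LogMAR 1.0 or above. An eye last measured near 0 and carried forward, when it would have fallen to at least 1.0, moves its arm mean by at least 1.0/45 = 0.022, in favour of whichever arm it belongs to.

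**Text set side by side.**
- SAP 13.1.3 describes days 518 to 699 as the protocol's window. The protocol's Visit 12 window is 548 ± 30, that is 518 to 578.
- The SAP 5.3 windows are contiguous (309–517, 518–699, 700–912). An eye with nothing in 518–699 therefore has only data belonging to another visit, and the choice between an earlier and a later value is open.
- SAP 13.2.2 refers to a method that SAP 13.1.3 does not contain.
- SAP 13.2.1 carries responders forward; SAP 13.2.2 says categorical endpoints are not imputed.
- SAP 13.2.1 extends the 13.1.3 strategy to later visits, after the sponsor and CRO are unmasked at 1.5 years (Protocol 13.11).

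**The case against.** Several safeguards stand. SAP 3.4, item 1, says a data review committee judged data collected before or after 1.5 years to be representative of the missing value. That points to observed off-window measurements, so the inference that values are invented is not supported. The decision precedes database lock, formal unmasking follows the interim lock (SAP 3.6), and Protocol 13.11 keeps study-conduct and data-management staff masked until then. The observed-data MMRM is not the only check: the primary model is repeated on the per-protocol set, where missing data are not imputed (SAP 4.4 and 13.1.5).

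On direction, REVERSE supports improvement in treated eyes, and with equal missingness the bias still runs against GS010. The natural-history study in Protocol 6.1, with no significant mean change, does not undercut the SAP either: if untreated eyes stay flat, LOCF can only penalise GS010. The documents report no imbalance in missingness.

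Three stronger readings are tempting and not supported:
- A shift near 0.1 LogMAR needs several eyes, all not yet affected, all heading for count fingers and all in one arm. The documents give no proportion of such eyes.
- The version log dates a change to missing-data handling to 17 February 2023, from which one might infer that the 1.5-year rule was altered after unmasking. The entry does not say what changed.
- The year-5 analysis on the last available value is not strictly identical to LOCF, because the main rule starts with a clinical decision and takes the record closest to target within a window.

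These points limit the likely size. They do not supply a selection rule, restore an MNAR analysis or reconcile the sections: the MMRM relies on MAR, and the per-protocol repeat makes no MNAR assumption.

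**Conclusion.** The concern holds in a limited form. The protocol's primary imputation was replaced by a step without a stated rule, followed by LOCF, and the claim that LOCF disadvantages GS010 is conditional. On REVERSE means the bias is slightly against GS010 under equal missingness. It turns in favour of GS010 only when placebo missingness is about 1.2 times (last value near baseline) to 2 times (last value near Week 48) that of GS010. Nor is the direction assured for not-yet-affected or very recently affected eyes, which the SAP's own rationale excepts.

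At the planned dropout below 5% the effect is small. It grows only if missingness is larger or uneven, or if near-normal eyes are carried forward. The calculation assumes that REVERSE means transfer to this trial, although REVERSE enrolled eyes with more than six months of vision loss. No missing-data counts are given. The documents do not support a conclusion that the planned analysis favours GS010.

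**What to change.** 1. Run the protocol's multiple imputation (MAR and MNAR) for the 1.5-year contrast and report it beside the clinical-decision/LOCF result. Add a placebo-reference or tipping-point analysis and a run restricted to days 518–578. Reporting side by side is preferable to installing a new primary model, because SAP version 10.0 (October 2024) post-dates the 1.5-year analysis.
2. Replace the clinical decision with a fixed rule, for example the observed value nearest Day 548. Where values were already settled at data review, list each with its source visit and show the effect of the fixed rule. Do not use clinical decision at visits after the 1.5-year unmasking.
3. In SAP 3.4, remove the statement that LOCF disadvantages GS010, or limit it to the conditions under which it holds.
4. Correct the window label in SAP 13.1.3, delete the reference to control-based imputation in 13.2.2, and use one responder rule in 13.2.1 and 13.2.2, derived from the imputed LogMAR.
5. At year 5 add an observed-data MMRM, because the last-available-value analysis largely repeats LOCF.

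The cost is SAP wording, modest programming and slightly wider intervals.

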13.1.4. Primary analysis of primary efficacy variable(s)

The primary analysis will be performed on the ITT population on the planned treatment (as randomized). The primary endpoint is the change from baseline of the BCVA, reported in LogMAR at 1.5 years post-treatment. Descriptive statistics will be presented for the baseline and 1.5 years post-treatment timepoints as well as for the change from baseline to the 1.5 years post-treatment based on data after imputation.

The treatment difference will be assessed with an ANCOVA model which includes terms to adjust for the baseline LogMAR value and includes treatment group as a fixed effect.

The analysis will be performed using a significance level of 0.05 (two-sided).

SAS code:

ARM =subject Treatment arm; change=Logmar change from baseline of second-affected/not-yet-affected eyes; Logmar0=Logmar at baseline

```
proc mixed data=XXX_;
class ARM;
model change=ARM logmar0 /s CL;
estimate " GS010 arm vs Placebo arm" ARM -1 1;
run;
```

13.1.5. Supportive analysis of primary efficacy variable(s)

Shift table and Mac Nemar test between Eyes on-chart/off-chart for LogMAR BCVA at baseline and Eyes on-chart/off-chart for LogMAR BCVA at 1.5 years by arm will be performed.

The primary analysis with the same model will be repeated for the following:

1. Using the mITT population, if different from the ITT population
2. Using the PP population
3. Same analyses will be conducted on the LogMAR instead of the change of LogMAR (analyses will be not adjusted on LogMAR at baseline but with duration from vision loss)

Using a model at the subject level, with repeated values for eye. We need to have comparison between treatment group (GS010 vs Placebo) and comparison between GS010 eye in GS010/ GS010 ARM and GS010 eye in GS010/ Placebo ARM.SAS code:

ID=identifiant; TREAT =(Placebo in GS010/ Placebo ARM / GS010 in GS010/ Placebo ARM / GS010 first affected eye in GS010/ GS010 ARM / GS010 second affected eye in GS010/ GS010 ARM ; change=Logmar change from baseline; Logmar0=Logmar at baseline;

```
proc mixed data=XXX ;
class ID TREAT (ref="PLACEBO") ;
model change= TREAT logmar0 /s CL;
random intercept/sub=ID type=AR(1);
lsestimate TREAT " GS010 vs Placebo " 1 1 1 -3/cl divisor=3;
lsestimate TREAT " GS010 in GS010/GS010 ARM vs GS010 in GS010/Placebo ARM" -2
1 1 0/cl divisor=2;
run;
```

4. Primary ITT analysis adjusted on potential confusion factors:

ANCOVA will be used to analyze the effect of treatment on the change from baseline of the BCVA, reported in LogMAR at 1.5 years post-treatment adjusted on baseline LogMAR value, and potential confusion factors. A backward selection approach will be considered to keep significant covariates among: Gender, Age at onset of the disease, Duration of vision loss, Pediatrics/Adults, Previous Idebenone treatment, BCVA at baseline as a continuous parameter, BCVA on-chart/off-chart at baseline, BCVA on-chart/off-chart at nadir, LogCS at baseline as a continuous parameter, LogCS on-chart/off-chart at baseline, LogCS on-chart/off-chart at nadir, baseline GCL volume, baseline Quadrant Temporal RNFL, baseline PMB RNFL and Region. We will consider a p-value of <0.2 in univariate model (adjusted on logMAR at baseline) for entry in the multivariate model and a p-value of >0.05 for removal from multivariate model. If a covariable has a p-value>0.05 but

causes a strong variation in the estimates of the treatment (+/-20%), then it will be conserved in the model and considered as a confounding factor. If linear hypothesis between change from baseline and quantitative variable is not verified, thus quantitative variable should be included in the model as qualitative variable (on the covariate's quartiles for example). Multicollinearity of independent variables (those which enter in the multivariate model) was checked via the variance inflation factor (VIF) statistic. If $VIF > 10$ between two or several covariables, only one covariable should be included in the model.

SAS code:

ARM =subject Treatment arm; change=Logmar change from baseline of second-affected/not-yet-affected eyes; Logmar0=Logmar at baseline; VARi=quantitative covariables i; VARCi=qualitative covariables i

Univariate analysis for quantitative variable:

```
proc mixed data=XXX;
model change= logmar0 VARi/s CL;
run;
```

Univariate analysis for qualitative variable:

```
proc mixed data=XXX;
class VARCi;
model change= logmar0 VARCi /s CL;
lsmeans VARCi;
run;
```

Multivariate analysis:

```
proc mixed data=XXX;
class ARM VARC1 VARC2 ...;
model change=ARM logmar0 VARC1 VARC2... VAR1 VAR2 .../s CL;
run;
```

Test of multicollinearity:

```
proc reg data= XXX;
model change= ARM logmar0 COUNTRY VAR1 VAR2 VAR3 /VIF TOL COLLIN;
run;
```

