## 9. Study Plan

### 9.1 Study Design

GS-LHON-CLIN-05 is a Phase III, global, multicenter, randomized, double-masked for the primary analysis, placebo-controlled, clinical study. As LHON is a neurodegenerative disease, the goal is to administer GS010 as soon as possible upon confirmation of the LHON diagnosis and the causative mutation.

All subjects will receive a peri-treatment, systemic immune modulating regimen for the prevention or diminution of ocular inflammation related to IVT injection of GS010 (please see Section 13.9.1 for full details).

At the Screening Visit (Visit 1), the duration of vision loss of each eye of each subject will be determined and documented. The eye with the longest duration of vision loss will be the first affected eye and the eye with the shortest duration of vision loss will be the second affected eye. Eyes that have not yet experienced clinically manifested decline in visual acuity will have a value of zero days for vision loss duration and will be considered “not yet affected” eyes. As all subjects are required to have clinically manifested vision loss due to *ND4* LHON to any extent in at least one eye, each subject will thus have one eye designated as the “first affected” eye and one eye designated as the “second affected/not yet affected” eye. Subjects may report simultaneous onset of vision loss in both of their eyes, indicating true simultaneous onset of vision loss or inability of the subject to distinguish which is the first affected eye and which is the second affected eye. For these subjects, vision loss duration will be equal for both eyes.

[figure not shown]
At the Inclusion Visit (Visit 2), new onset vision loss occurring since the Screening Visit (Visit 1) in an eye previously unaffected by clinically manifested visual acuity loss will be documented and vision loss duration will be recorded. The best-seeing and worst-seeing eye of each subject will be determined, based on the baseline vision testing performed at Visit 2. A pre-defined algorithm, detailed in Section 13.10.1, to determine the best- and worst-seeing eyes will be employed.

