Subjects meeting all eligibility criteria for selection and inclusion will be randomized to treatment arm 1 (TARM1) or treatment arm 2 (TARM2) in a 1:1 allocation (see Figure 1). Subjects in TARM1 will receive intravitreal GS010 in their first affected eye and their second-affected/not-yet-affected eye. Subjects in TARM2 will receive intravitreal GS010 in their first affected eye and placebo intravitreal injection in their second- affected/not-yet-affected eye. For subjects who report simultaneous onset of vision loss in both eyes, the right or left eye will be selected randomly to serve as the second-affected/not-yet-affected eye.

If the right eye is selected randomly as the second-affected/not-yet-affected eye, the left eye will be designated as the first affected eye, and vice versa.

Figure 1: Study Treatment Arms; Post-Treatment Follow-up Period 1: up to 2 years post-treatment

Administration of an Intra ocular pressure (IOP) lowering agent of the investigator's choice will precede all intravitreal injections. Pre-intravitreal injection procedural preparation will include pupil dilation, topical antisepsis, and topical anesthesia. The IMPs (GS010 and placebo) will be administered with a standard intravitreal injection procedure. Each eye will undergo administration of the allocated treatment with a single intravitreal injection, performed as a separate procedure. Please refer to the Intravitreal GS010/Placebo Injection Guide for full details.

Per the Investigator's discretion and according to local standard accepted medical practices, treatment administration to both eyes may be performed at a single Treatment Visit (Visit 3) (i.e. intravitreal injection of both eyes of a given subject is performed the same day as two separate procedures) or may be performed on two consecutive days (i.e. one eye of the subject will be administered the allocated treatment one day and the next day the fellow eye of the subject will be administered the allocated treatment).

Inclusion Visit (Visit 2) vision test results will serve as the baseline values for both eyes of a given subject when the treatments are administered on the same day and when they are administered on consecutive days. Study Day 0 is the day that treatment administration is completed to both eyes; in the setting of treatment administration on consecutive days, this will be the second treatment day. The timing of visits and visit

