6.5. Covariance of subgroups

For the MMRM model, LMM and GLMM, autoregressive (AR(1)) covariance structure will be used to model the within-patient error and the Kenward-Roger approximation will be used to estimate the degrees of freedom. If the model assuming AR(1) covariance structure fails to converge, the following covariance structures will be tested one after the other in the order listed until one converges (remaining covariance structures will not be tested): heterogeneous autoregressive order 1 (ARH(1)), compound symmetry, heterogeneous compound symmetry (CSH), Toeplitz (TOEP), and heterogeneous Toeplitz (TOEPH).

7. Output presentations

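### The two-eye supportive model in SAP 13.1.5 gives first and second affected eyes one residual variance, so both coded contrasts have wrong standard errors if the two kinds of eye differ in spread

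*SAP*

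**What the plan says.** SAP 13.1.5 announces the analysis with the words "Using a model at the subject level, with repeated values for eye". The class variable TREAT has four levels: placebo eyes and GS010 eyes in the GS010/placebo arm, and first and second affected eyes in the GS010/GS010 arm. The fixed part is "model change= TREAT logmar0 /s CL". The only covariance statement is "random intercept/sub=ID type=AR(1"). There is no REPEATED statement, no GROUP= option and no Kenward-Roger option in this block.

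Two contrasts are coded. The first sets the average of the three GS010 groups against placebo (`1 1 1 -3`, divisor 3). The second sets the average of the two GS010 groups of the bilateral arm against the GS010 eye of the other arm (`-2 1 1 0`, divisor 2).

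SAP 6.5 applies AR(1) and Kenward-Roger to the MMRM, LMM and GLMM. It moves to other structures, including heterogeneous ones, only on this condition: "If the model assuming AR(1) covariance structure fails to converge".

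On the eyes themselves, SAP 3.1 states: "Subjects in TARM2 will receive intravitreal GS010 in their first affected eye and placebo intravitreal injection in their second- affected/not-yet-affected eye". Protocol 9.1 adds: "Eyes that have not yet experienced clinically manifested decline in visual acuity will have a value of zero days for vision loss duration".

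**The concern.** The text promises repeated values per eye, but the code fits a shared intercept plus one common residual variance. With a single intercept per subject, the random-effect covariance matrix has one element, so AR(1) has nothing to act on. ARH(1), CSH and TOEPH on the same statement would leave the residual variance common too. In any case they are tried only after non-convergence, which unequal variance does not cause.

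The pooling matters because eye order and treatment are not balanced. Every placebo eye is a second eye, while two of the three GS010 groups are first eyes. The pooled variance is the average over both kinds of eye, and each contrast weights them unequally. At stake are the intervals and p-values of one supportive analysis of the primary endpoint, which could look firmer or weaker than the data warrant.

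**Working it through.** **Inputs from the documents.** SD 0.50 after baseline adjustment, effect 0.3 LogMAR, 80% power, 45 evaluable subjects per arm (SAP 3.2); two-sided 5% level (SAP 13.1.4).

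**Assumptions.** Second-eye SD s2 = 0.50. Ratio s2/s1 from 0.8 to 2, where s1 is the first-eye SD. Between-eye correlation rho = 0.5, varied from 0 to 0.7. TREAT levels are ordered so that placebo is last and the GS010 eye of the GS010/placebo arm is first, as the contrast coefficients imply.

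**The plan's own figure.** 2 × (1.96 + 0.842)² × (0.50/0.30)² = 43.6, so 44 per arm by the normal approximation. The noncentral t gives 45 (power 0.804; 0.795 at 44). The stated 45 reproduces.

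**Variance of each contrast.** Write c = rho × s1 × s2 and n = 45. The fitted model replaces both s1² and s2² by (s1² + s2²)/2 and keeps c.

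Contrast `1 1 1 -3`:
- True: [(2/9)s1² + (10/9)s2² − (4/9)c]/n
- Model: [(6/9)(s1² + s2²) − (4/9)c]/n
- True minus model: (4/9)(s2² − s1²)/n

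Contrast `-2 1 1 0`:
- True: [(5/4)s1² + (1/4)s2² + (1/2)c]/n
- Model: [(3/4)(s1² + s2²) + (1/2)c]/n
- True minus model: (1/2)(s1² − s2²)/n

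Neither difference depends on the correlation, and they have opposite signs.

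**Example, ratio 1.5.** s1 = 0.333, s1² = 0.1111, s2² = 0.25, c = 0.0833. For `1 1 1 -3`, the true variance is (0.0247 + 0.2778 − 0.0370)/45, SE 0.077. The model variance is (0.2407 − 0.0370)/45, SE 0.067. The SE ratio is 0.876, and 2 × [1 − Φ(1.96 × 0.876)] = 0.086.

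**Results at rho = 0.5** (normal approximation; type I error = 2 × [1 − Φ(1.96 × model SE / true SE)]):

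| s2/s1 | `1 1 1 -3`: true SE, model SE | Type I error | `-2 1 1 0`: true SE, model SE | Type I error |
|---|---|---|---|---|
| 0.8 | 0.081, 0.089 | 3.1% | 0.118, 0.111 | 6.5% |
| 1 | 0.079, 0.079 | 5.0% | 0.099, 0.099 | 5.0% |
| 1.25 | 0.077, 0.071 | 7.1% | 0.083, 0.089 | 3.6% |
| 1.5 | 0.077, 0.067 | 8.6% | 0.073, 0.083 | 2.6% |
| 2 | 0.077, 0.063 | 10.5% | 0.062, 0.077 | 1.5% |

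Over correlations 0 to 0.7, the placebo-contrast figures range from 6.7% to 7.2% at ratio 1.25, 8.0% to 8.9% at 1.5, and 9.8% to 10.9% at 2.

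**Simulation check.** REML fits with baseline LogMAR as covariate (400 runs per setting, rho 0.5) gave 5.5%, 6.5%, 8.5% and 9.8% for the placebo contrast at ratios 1, 1.25, 1.5 and 2. With s1 = 0.5 and s2 = 0.4 (ratio 0.8) the rate was 3.3%. An unstructured 2×2 eye covariance gave 4.5% to 5.0% in every setting.

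**The case against.** The strongest reply is that the premise is not in the documents. The only SD is a single figure, not split by eye order, and at equal SDs there is no error. Several features pull the two kinds of eye together:
- Every affected eye must be within 365 days of onset (Protocol 10.2).
- In the natural-history cohort cited in Protocol 6.1, 53% were bilateral within 2 months and 80% within 6 months.
- For simultaneous onset, the second eye is chosen at random (Protocol 13.10).
- Off-chart eyes get fixed values of 2.0 or 2.3 for counting fingers or hand motion (SAP 13.1.1).
- Baseline LogMAR is in the model.

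This stands as a limit on size. It does not show equal variances. Second eyes can include eyes with no vision loss yet, and Protocol 6.1 reports a final acuity of 20/200 or worse in 98% of eyes, so some have far to fall. The ratio is unknown.

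It is also fair that this is one supportive model with no decision rule, and that all alpha is spent on the primary analysis (SAP 6.3).

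A reader might infer that the model overstates the evidence for GS010, or could confirm a benefit that the primary analysis does not show. The documents do not support that. Nothing in them establishes that second eyes vary more, the placebo contrast is conservative if first eyes do, and a supportive p-value cannot replace the primary test.

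**Conclusion.** The covariance statement does not do what SAP 6.5 intends, and the fitted model has one residual variance for eyes that may differ in spread. This follows from the code. The consequence is conditional: both contrasts have wrong standard errors whenever the two SDs differ, and correct ones when they are equal.

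The size rests on the assumed ratio. For GS010 versus placebo it runs from mildly conservative (about 3% at 0.8) to about double the nominal level (10-11% at 2). The within-GS010 contrast errs the other way. The type I error figures for `1 1 1 -3` also presuppose that first and second eyes have the same mean adjusted change. If they do not, the estimate mixes eye order with treatment, which is a separate matter.

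Only this model's intervals and p-values are affected. The primary ANCOVA (SAP 13.1.4) and the MMRM (SAP 13.1.6) use second eyes only, and the sample size does not depend on this model. The correction is worth making because it is cheap and needs no view on which eye varies more.

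**What to change.** In the two-eye model of SAP 13.1.5:
- Replace the RANDOM line with `repeated EYE / sub=ID type=UN;`, where EYE is first affected or second affected/not yet affected, and add EYE to the CLASS statement.
- Add `ddfm=kenwardroger` to the MODEL statement, as SAP 6.5 already requires.
- State in SAP 6.5 that this two-record model is exempt from the AR(1)-first rule.

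SAP 5.3 speaks of visits made after the year 1.5 analyses, and unmasking was planned for that analysis, so the change comes after unmasking. Report the by-eye version beside the existing output, labelled as a documented correction, and show the estimated SD for each kind of eye.

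The cost is a few words of code, one SAP sentence, one extra covariance parameter estimated from about 90 subjects, and possibly a slightly wider interval. The change corrects standard errors only. It does not separate eye order from treatment in the `1 1 1 -3` contrast.
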